#### **7.1.2 Clinical Investigation Plan (CIP) Deviations**

All protocol deviations will be presented in the listings.

#### **7.1.3 Analysis Sets**

All enrolled subjects will be included in the safety analysis population.

### **7.2 General Methodology**

All data collected from the time of screening until the end of the study will be collected either on eCRFs or electronically by uploading the various devices. Data and analysis will be summarized in a Clinical Study Report.

### **7.3 Center Pooling**

Data will be pooled for analysis.

### **7.4 Handling of Missing, Unused, and Spurious Data and Dropouts**

In the case of partially missing day and/or month, the first day of the month will be used for event dates with known year and month but unknown day, unless specified otherwise in the description; similarly, the first day of the year will be used for event dates with known year but unknown month and day, unless specified otherwise.

In the case of partially missing time, 12am will be used for event times with known day but unknown time, if applicable.

No additional imputation will be applied for the missing data.

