	
○ Administer EOS questionnaire Note: EOS questionnaires will be administered to all subjects at the end of their participation in the study. This includes subjects who are terminated or who voluntarily discontinue participation in the study.○ Return study meter, transmitter, wearables and sponsor-provided smartphone○ Wipe data off (perform factory reset) wearables
--	---

Medtronic Business Restricted

Figure 1. Study Visit Schedule for Phase 1 and Phase 2, 90 Days and 280 Days of Guardian Connect system Wear

Safety and Monitoring/Risk Analysis	Safety monitoring/risk analysis details are outlined in Section 10 .
Device Deficiencies	Device deficiencies reported directly to the investigational center staff by a subject should either be reported to the Medtronic support line by the subject or investigational center staff. All applicable device deficiencies that are reported to the Medtronic support line will be documented. Depending on the study device or app, the subject and/or investigational center may be instructed by the support line to contact the respective device manufacturer. Device deficiencies for commercially released devices or apps should be captured according to local regulatory requirements and is the responsibility of the Investigator. For additional information, see Section 11.8 .
Subject Stopping Rules	Refer to Section 9.10 on “Subject Exit, Withdrawal or Discontinuation”.
Study Stopping Rules for Entire Study	There are no predefined study stopping rules.

Statistical Analysis for Endpoints and Hypothesis	
During Phase 1 and Phase 2
 
Primary Endpoint Descriptive statistics will be performed; no statistically powered analyses or hypothesis testing will be performed.
 
• Glycemic control: Percentage of Time in Range (SG <70 mg/dL, 70-180 mg/dL, and >180 mg/dL) 
Other Descriptive Endpoints
 
• Summary of completed data collection/available data• Summary of study questionnaire results 
Safety Descriptive summary will be used to characterize safety events:
 
• Serious adverse events (SAE)• Device related adverse events (AEs)• Procedure related AEs• Serious adverse device effect (SADE)• Unanticipated adverse device effect (UADE)• Severe hypoglycemia• Diabetic ketoacidosis (DKA) 
Device Deficiencies Descriptive summary will be used to characterize device deficiencies.

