10.5 Risk Determination

In the opinion of the sponsor, this study is considered to be a non-significant risk (NSR) study. Results of an evaluation of the requirements per 21 CFR Part 812.3, led to the NSR determination as follows:

- The devices are not intended as an implant and do not present potential for serious risk to subject health, safety, or welfare.
- The devices are not to be used for supporting or sustaining human life and do not present potential for serious risk to subject health, safety, or welfare.
- The devices are not for a use of substantial importance in diagnosing, curing, mitigating or treating disease, or otherwise preventing impairment of human health and do not present potential for serious risk to subject health, safety, or welfare.
- Review of the device risk analysis did not identify potential for serious risk to subject health, safety, or welfare.

The NSR determination is also based on the commensurate safety experience of continuous glucose monitoring in commercial use. Furthermore, subjects should be instructed to make all treatment decisions based on a fingerstick glucose measurement and not on sensor glucose information provided by CGM system.

11 Adverse Events and Device Deficiencies

Throughout the course of the study, investigational centers will make all efforts to remain alert to possible reportable adverse events (AEs) or untoward findings. The study personnel will elicit reports of AEs from the subject at each visit (including phone calls) starting at the time of signing the informed

Medtronic Business Restricted

consent documenting the medical diagnosis, date of event start and end, causality (relationship to device or procedure), treatment, outcome, and description that includes the details of the event.

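### Does dating every partial event to the first of the month or year (SAP 7.4) distort the planned safety results?

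*SAP*

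**What the plan says.** SAP 7.4 gives three rules and a closing sentence.

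- Day unknown: "the first day of the month will be used for event dates with known year and month but unknown day". Room is left for exceptions.
- Day and month unknown: "the first day of the year will be used for event dates with known year but unknown month and day, unless specified otherwise".
- Time unknown: "12am will be used for event times with known day but unknown time, if applicable".
- Beyond that: "No additional imputation will be applied for the missing data".

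The term for event dates is not defined, and neither document writes out an exception. The opening paragraph of Protocol Section 11 has sites elicit adverse events from the signing of consent and record, among other items, "date of event start and end, causality (relationship to device or procedure), treatment, outcome". Both ends of each event are therefore collected.

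The outputs are set elsewhere. SAP 7.10.1 and Protocol 13.8 plan a descriptive summary by category: serious, device related, procedure related, serious device effects, unanticipated device effects, severe hypoglycemia and ketoacidosis. SAP 7.1.3 puts every enrolled subject in the safety population. SAP 7.9.1 plans descriptive statistics for sensor time in range, without hypothesis tests.

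**The concern.** An earliest-date rule is a common default for onsets, but it works badly for end dates. An event that starts on 10 March and ends on 14 March, with the end day missing, gets an end of 1 March, nine days before it began. For onsets, the device goes on at Visit 2, up to 14 days after consent. An onset moved to the first of the month or year can then precede the device, or consent itself. An early Phase 2 onset can slide into Phase 1, and Phase 2 is a selected group of adults. A 12am time on the day of Visit 2 would put an insertion-site event ahead of the insertion.

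Safety description is one of the few planned outputs of this single-arm study. If the tables relied on these dates, device-related events could be lost as preceding exposure, durations could turn negative, and events could be credited to the wrong phase.

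**Working it through.** The documents state no figure on this point, so there is nothing to reproduce. The check has two parts: how often the rule misplaces a date, and whether any planned output uses the date.

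**How often, given that a date is partial.** Assumptions not in the documents: Visit 2 (or the event start) is equally likely on each of 365 days, and onset is uniform over follow-up. Month lengths *m* are 31 (seven months), 30 (four) and 28 (one).

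*End day missing, start known, event lasting D days.* The imputed end precedes the start when both fall in the same month and the start is not the 1st. For D below 28 the count is 365 − 12(D + 1).

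| D (days) | Count | Share of 365 |
|---|---|---|
| 3 | 365 − 48 = 317 | 87% |
| 7 | 365 − 96 = 269 | 74% |
| 14 | 365 − 180 = 185 | 51% |

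At 30 days the share is 0%.

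*Onset day missing, dated before Visit 2.* The pairs at risk number Σ m(m − 1)/2 = 7 × 465 + 4 × 435 + 378 = 5373, out of 365 × L for follow-up of L days.

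- L = 30: 5373/10,950 = 49%
- L = 100: 5373/36,500 = 15%
- L = 280: 5373/102,200 = 5%

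*Onset day missing, dated before a consent 14 days earlier (the extreme gap).* The count is Σ (m − 15)(m − 14)/2 = 7 × 136 + 4 × 120 + 91 = 1523, which gives 4.2% over 100 days and 1.5% over 280.

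*Onset known by year only, dated before Visit 2.* The count is 364L − L(L − 1)/2.

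- L = 100: 31,450/36,500 = 86%
- L = 280: 62,860/102,200 = 62%

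*True Phase 2 onset (Days 91–280, 190 days) moved to Day 90 or earlier.*

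- Month known: 5373/69,350 = 7.7%
- Year only: (364 × 190 − 190 × 189/2)/69,350 = 51,205/69,350 = 74%

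**Whether a planned output uses the date.**

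- *Counts by category (SAP 7.10.1).* Events are collected from consent and the population is all enrolled subjects. No rule drops an event that precedes the device, so a shifted onset changes no count.
- *Device and procedure relatedness.* Protocol 11.5 has the investigator assign one of five categories from the subject's account, device uploads and medical records. Under Protocol 12.1 the clinical events committee reviews serious events, serious and unanticipated device effects, severe hypoglycemia and ketoacidosis, and its classification is the one analysed. Neither judgement is derived from an imputed date.
- *Duration.* No duration summary is planned.
- *Phase.* The Synopsis heading "During Phase 1 and Phase 2" stands once over all endpoint and safety summaries. It covers both phases together, and no by-phase adverse event table is defined.
- *Time.* A 12am entry leaves the date unchanged, so it cannot move an event between phases. Protocol Section 11 asks for start and end dates, and the rule applies only where a time is relevant.
- *Time in range (SAP 7.9.1).* It is computed from sensor glucose values, not event dates.

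**The case for a change.** The strongest reply is that the rule is wrong on its face and cheap to mend. If no output uses imputed dates, it serves no purpose; if any does, some dates will be invalid. A dataset that shows a device-related event before the device contradicts the causality it reports, since timing is among the criteria in Protocol 11.5. The escape clauses offer little help, because no exception is written.

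Much of this stands. The missing split between start and end dates is a real gap. It could surface in a listing, or in a later duration or by-phase summary. But those are outputs the plan does not contain, and an analyst who produced one would meet the negative durations at once and bound the dates.

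The larger percentages also need an unlikely input. A year-only onset would have to survive a prospective study of 100 or 280 days in which events are elicited at each visit and call (Protocol Section 11), source documents are obtained (Protocol 11.2) and incomplete data are queried (Protocol 15.6.1.4). For month-only onsets, 85% to 95% stay on or after Visit 2 over 100 to 280 days.

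Nor is the obvious remedy free of gaps. Enrolment occurs at consent (Protocol 7.2), so a subject who leaves before Visit 2 is in the safety population with no Visit 2 date at which to floor an onset.

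**Conclusion.** The observation about SAP 7.4 is correct, but it calls for no change. One earliest-date rule for starts and ends can put an end before its start (87%, 74% and 51% of events lasting 3, 7 and 14 days) and can put an onset before Visit 2 (15% of month-only onsets over 100 days). All of these are conditional on a partial date and on evenly spread calendar dates; the documents do not say how many partial dates to expect. Followed as written, the plan yields the same event counts, relatedness categories and time-in-range summaries whichever day is imputed, so rewriting the rule would improve no planned result. This conclusion rests on the outputs staying as listed in SAP 7.9 and 7.10. If a duration, device-emergent or by-phase table were added later, that analysis would need its own start and end conventions.

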### **7.5 Adjustments for Multiple Comparisons**

No adjustments will be made.

## 7.6 Demographic and Other Baseline Characteristics

Subject characteristics, including age, gender, race, ethnicity, type of diabetes mellitus, and BMI (calculated based on provided height and weight) will be summarized by descriptive statistics

## 7.7 Treatment Characteristics

Not applicable.

## 7.8 Interim Analyses

No interim analysis will be conducted.

## 7.9 Evaluation of Objectives

### 7.9.1 Endpoints

Descriptive statistics will be performed; no statistically powered analyses or hypothesis testing will be performed.

- Glycemic control: Percentage of Time in Range (SG <70 mg/dL, 70-180 mg/dL, and >180 mg/dL)

### 7.9.2 Other descriptive Endpoints

- Summary of completed data collection/available data
- Summary of study questionnaire results

## 7.10 Safety Evaluation

### 7.10.1 Adverse Events (AE)

Descriptive summary will be used to characterize adverse events:

- Serious Adverse Events (SAE)
- Device Related AEs
- Procedure Related AEs
- Serious Adverse Device Effect (SADE)
- Unanticipated Adverse Device Effect (UADE)
- Severe hypoglycemia
- Diabetic Ketoacidosis (DKA)

### 7.10.2 Device Deficiencies

Descriptive summary will be used to characterize device deficiencies.

## 7.11 Health Outcomes Analyses

Not applicable.

## 7.12 Changes to Planned Analysis

Not applicable.

## 8. Validation Requirements

Level I or Level II validation are required for analysis output. Level I requires that the peer reviewer independently programs output and then compares the output with that generated by the original Statistical Programmer. Level II requires that the peer reviewer reviews the code; where appropriate, performs manual calculations or simple programming checks to verify the output.

